- Exclusion of participants with known autoimmunity also applies as they could be at risk for exacerbation of their condition by the administration of therapies that relieve immune suppression such as BMS-986258 and nivolumab.
- Participants will be observed frequently for clinical evaluation and blood counts during dose escalation.
- Well-defined discontinuation criteria are established in the protocol for individual participants for both safety and treatment futility with clear criteria for treatment discontinuation, dose delay, and toxicity management.
- For the combination therapy with nivolumab, management algorithms for immune-related events are well established based on the clinical experiences from the over 23,500 subjects who were exposed to nivolumab as either monotherapy or in combination with other agents, in the past as well as in ongoing studies.

5.2 **Number of Participants**

[figure not shown]
The approximate number of participants will be up to as shown below. Part A Monotherapy Escalation: The total sample size is up to approximately including to assess the MTD/MAAD and an additional in NSCLC PD cohorts. Part A1: SC Dose: The total sample size is up to approximately participants to evaluate up to dose levels. Part B Combination Escalation: The total sample size is up to approximately participants, participants to assess the MTD/MAAD in combination and in NSCLC PD including cohorts.

Part C Cohort Expansion: Approximately up to participants will be treated in each of the 5 tumor cohorts (up to a total of across tumors).

5.3 **End of Study Definition**

The start of the study is defined as the first visit for the first participant screened. Similarly, the end of the study is defined as the last visit or scheduled procedure shown in the Schedule of) for the last participant. Primary study completion is defined as the final date on which data for the primary endpoint are expected to be collected, if this is not the same.

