5.4.7 Rationale for Tumor Selection for Expansion (Part C)

Five tumor types were chosen for the study. The following specific populations may be chosen for Part C:

- RCC participants who received and progressed on or after anti-PD-1 therapy as monotherapy or in combination with other I-O agents)
- MSI-H CRC participants who received and progressed on or after-anti-PD-1 therapy, and MSS CRC participants
- NSCLC participants who received and progressed on or after-anti-PD-1 therapy
- SCCHN participants who received and progressed on or after anti-PD-1 therapy
- Recurrent or metastatic TNBC participants

The precise indications that will be evaluated in these tumor types were defined based on current results (or lack of) with immune-oncology agents, but also on the premise that TIM-3 and PD-1 are frequently co-expressed and TIM-3 may arise as a mechanism of resistance for anti-PD-1 therapy.

Given its inherent immunogenic characteristics, RCC was among the first tumor types to be studied in the context of immunotherapy. High-dose IL-2 was approved in 1992 for the treatment of RCC and remained an important treatment option for 2 decades. More recent discoveries of molecular and immunological alterations led to the approval of nivolumab for previously treated advanced RCC, based on an ORR of 25% in comparison with 5% for everolimus. Recently published results demonstrated response rates of around 40% with the combination of nivolumab and ipilimumab for patients with metastatic RCC. Progress is being made, but despite recent advances, most patients with advanced RCC will succumb to their disease.

The current standard treatment for patients with metastatic CRC is fluorouracil-based chemotherapy regimens combined with agents targeting angiogenesis or epidermal growth factor receptor (EGFR). ⁵⁴ Based on results from the Phase 2 CheckMate-142 trial, nivolumab was

Protocol Amendment No.: 07

approved for the treatment of patients with MSI-H or mismatch repair-deficient (MMR-D) metastatic CRC⁵⁵ but MSI-H patients correspond to 5% of the patient population with metastatic CRC. MSS colon cancers, which make up the majority of the tumors, do not respond to anti-PD-1 monotherapy. TIM-3 is expressed in the immune infiltrate in CRC; therefore, BMS-986258 may be active in this indication.

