- ii) Participants with MSS CRC must have received and then progressed on or after, or have been intolerant or refractory to, at least 1 standard systemic therapy for metastatic and/or unresectable disease (or have progressed within 6 months of adjuvant therapy), including oxaliplatin and irinotecan.
 - Participants must have known microsatellite instability or mismatch repair status. V-Ki-ras2 Kirsten rat sarcoma viral oncogene homolog, and B-Raf proto-oncogene status, if known, should be documented; if unknown, participants must consent to allow their submitted archived tumor tissue sample (block or unstained slides) to be tested, in addition to the required fresh tumor biopsies.
- iii) Participants who have received prior anti-angiogenic therapy (eg, bevacizumab) and/or anti-EGFR therapy (eg, cetuximab or panitumumab) are eligible.
- iv) Participants with MSI-H or MMR-D status must have received and progressed on or after anti-PD-(L)1 therapy, if available, for enrollment.
- v) Participants in Part C only, with MSI-H or MMR-D status, must have been resistant to anti-PD-(L)1 therapy. Refer to inclusion criteria 2) i) for the definition of anti-PD-(L)1 resistance.

f) Participants with NSCLC

- i) Histologically confirmed NSCLC meeting stage criteria for Stage IIIB, Stage IV, or recurrent disease.
- ii) Participants must have recurrent or progressive disease during or after platinum doublet-based chemotherapy for advanced or metastatic disease.

OR

Must have recurrent or progressive disease within 6 months after completing platinum-based chemotherapy for local disease.

- iii) Status for actionable mutations (eg, EGFR, ALK, ROS1, RET, etc.) must be known [when testing is available as per country/region standard of care practices]; participants with actionable mutations must have received and progressed on, have been intolerant to, or not be a candidate for, standard tyrosine kinase inhibitors [as available per country/region standard of care practices].
- iv) Participants must have received and progressed on or after anti-PD-(L)1 therapy, if available, for enrollment.
- v) Participants in Part A and B NSCLC PD cohorts and Part C only must have been resistant to anti-PD-(L)1 therapy. Refer to inclusion criteria 2) i) for the definition of anti-PD-(L)1 resistance.

g) Participants with SCCHN

- i) Histologically confirmed, recurrent, or metastatic SCCHN (oral cavity, pharynx, larynx) and not amenable to local therapy with curative intent.

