- ii) Participants who progressed on or after, or were intolerant to, a platinum-containing regimen.

iii) Prior curative radiation therapy must have been completed at least 4 weeks prior to first study drug administration. Prior focal palliative radiotherapy must have been completed at least 2 weeks before study drug administration.

- iv) Documentation of p16 is sufficient to determine HPV status of tumor for SCCHN of the oropharynx. Note: If results are not available, then a sample (tissue on microscopic slides, tissue block, or a fresh tissue biopsy in formalin) should be sent to the central laboratory for analysis.
- v) Participants must have received and progressed on or after anti-PD-(L)1 therapy, if available, for enrollment.
- vi) Participants in Part C only must have been resistant to anti-PD-(L)1 therapy. Refer to inclusion criteria 2) i) for the definition of anti-PD-(L)1 resistance.
- h) Participants with TNBC
 - i) Males and females with histologically confirmed TNBC as defined by American Society of Clinical Oncology/College of American Pathologists guidelines⁷⁴.
 - ii) Participants must have received and progressed on or after, or have been intolerant or refractory to, at least 1 standard chemotherapy regimen containing anthracycline and taxane; in addition, the participant must have received at least 1 regimen for the treatment of metastatic or locally advanced disease.
- i) Participants with anti-PD-(L)1 resistant RCC, CRC, NSCLC, and SCCHN, participating in Part C, Part A NSCLC PD, and Part B NSCLC PD cohorts only.
 - i) Participants must have received prior anti-PD-1/PD-L1 therapy and have radiologically or clinically documented disease progression or recurring disease on or within 3 months following last dose of anti-PD 1/PD-L1 therapy for their advanced (metastatic and/or unresectable) cancer and have been considered for all other potentially efficacious therapies prior to enrollment.
 - (1) One intervening systemic therapy is allowed between anti PD-(L)1 therapy and enrollment.
 - (2) Anti-PD-(L)1 therapies may have been received in sequential or combination regimens.
 - (3) Required documentation includes start and stop dates of prior anti-PD-(L)1 therapy and a progression date no more than 3 months after the last dose of anti-PD-(L)1 therapy.

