10.1.2 Cohort Expansion

The purpose of cohort expansion is to gather additional safety, tolerability, preliminary efficacy, PK, and PD information regarding BMS-986258 in combination with nivolumab. However, the sample size is strictly based on efficacy, specifically on the target ORR relative to historic response rate.

Part C will be an expansion phase for BMS-986258 in combination with nivolumab and may include participants with RCC, CRC, NSCLC, SCCHN, and TNBC. Enrolled participants with RCC, SCCHN, NSCLC and CRC MSI-H will be relapsed or refractory to prior PD-(L)1 treatment. Participants with a diagnosis of RCC, CRC, NSCLC, and SCCHN may be selected

Each disease cohort expansion will be handled independently and there will be no multiplicity adjustment. Up to participants may be treated per expansion cohort (for a total of in Part C overall) to allow for if needed per tumor cohort, although a total of up to participants need to be treated across tumor cohorts based on the sample size assumptions and characteristics in the 2-stage design shown below.

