10.3.1 Efficacy Analyses

The primary efficacy analyses (Table 10.3.1-1) will be performed on the treated population for the final analysis. Efficacy analyses based on the response-evaluable population may be performed for interim analyses when the minimum follow-up period is less than sufficient to warrant adequate interpretation of the result. Details of the censoring scheme on time-to-event endpoints such as DOR, PFS, and OS rate will be described in the Statistical Analysis Plan.

 Table 10.3.1-1:
 Efficacy - Statistical Analyses

Endpoint	Statistical Analysis Methods
ORR is defined as the proportion of population of interest whose BOR is either CR or PR per RECIST v1.1 BOR for a participant will be assessed per RECIST v1.1.	Estimate of ORR and corresponding 2-sided exact 95% CI by treatment for each tumor type.
Median DOR DOR for a participant with a BOR of CR or PR is defined as the time between the date of first response and the date of the first objectively documented tumor progression per RECIST v1.1 or death, whichever occurs first.	Median duration of response using the Kaplan-Meier method and corresponding 2-sided 95% CI by treatment for each tumor type.
PFS rate at 6, 9, and 12 months PFS for a participant is defined as the time from the first dosing date to the date of first objectively documented disease progression or death due to any cause, whichever occurs first.	Estimate by the Kaplan-Meier method and corresponding 95% CI will be derived for each tumor type.

Abbreviations: BOR, best overall response; CI, confidence interval; CR, complete response; DOR, duration of response; ORR, overall response rate; PFS, progression free survival; PR, partial response; RECIST, Response Evaluation Criteria In Solid Tumors.

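### Table 10.3.1-1 gives one CRC response rate for Part C; if both MSI-H/MMR-D and MSS participants are enrolled and respond differently, that rate depends on the mix and describes neither group

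*Combined protocol and SAP*

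**What the plan says.** Table 10.3.1-1 in Section 10.3.1 sets the reporting unit for ORR: "Estimate of ORR and corresponding 2-sided exact 95% CI by treatment for each tumor type". Median DOR follows the same unit, and PFS rates at 6, 9 and 12 months are given for each tumor type. The denominator is stated only in general terms: "ORR is defined as the proportion of population of interest whose BOR is either CR or PR per RECIST v1.1".

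Section 5.2 counts CRC as one cohort; a number of participants that is blacked out "will be treated in each of the 5 tumor cohorts". Section 5.4.7 lists the CRC populations that may be chosen for Part C under one bullet: "MSI-H CRC participants who received and progressed on or after-anti-PD-1 therapy, and MSS CRC participants". The same section gives MSI-H disease as 5% of metastatic CRC and says: "MSS colon cancers, which make up the majority of the tumors, do not respond to anti-PD-1" (the sentence continues with the word monotherapy).

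Eligibility differs between the two groups. Under Section 6.1, criterion 2e(v), MSI-H or MMR-D participants in Part C must be resistant to anti-PD-(L)1 therapy. Criterion 2e(ii) asks MSS participants for prior standard systemic therapy and sets no anti-PD-(L)1 rule. Section 10.1.2 repeats the distinction: "Enrolled participants with RCC, SCCHN, NSCLC and CRC MSI-H will be relapsed or refractory to prior PD-(L)1 treatment". Status is available for everyone: "Participants must have known microsatellite instability or mismatch repair status".

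Section 10.1.2 bases the Part C sample size on a target ORR against a historic rate, and Section 10.3.8 refers to a two-stage framework. The stage sizes, cut-offs and rates are blacked out.

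**The concern.** The protocol treats the two CRC groups as different diseases for this purpose. In MSI-H/MMR-D disease the question is whether adding BMS-986258 restores response after resistance to PD-(L)1 blockade. In MSS disease it is whether the combination produces responses where PD-1 blockade alone does not. One historic rate is unlikely to serve both questions, and one observed rate does not answer either of them.

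The visible text sets no quota, cap or separate row for the two groups. If both enter, the CRC estimate will partly reflect who happened to be enrolled. Activity confined to MSI-H disease could be hidden by a majority of MSS participants. A moderate pooled rate could also be read as activity in MSS disease when the responses came from the other group.

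**Working it through.** The visible text contains no CRC response rate, cohort size or decision boundary, so there is no figure of the plan's own to reproduce. The check has two parts.

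**1. Does the plan as written lead to a mixture?**

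- Reporting unit: tumor type (Table 10.3.1-1).
- CRC: one of five tumor cohorts (Section 5.2).
- Who may enter: MSI-H/MMR-D with resistance to anti-PD-(L)1, and MSS without that rule (Sections 5.4.7 and 6.1).
- Split or cap by MSI status in the visible text: none.

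Read together, these give one CRC estimate over both groups whenever both are enrolled. Section 10.3 presents results by study part, so Part C is not combined with Parts A and B. That does not separate the two groups within Part C.

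**2. How far can the mix move the estimate?**

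Let *w* be the MSI-H share of the CRC cohort, and *p*H and *p*S the true ORRs in MSI-H and MSS. Then

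pooled ORR = *w* × *p*H + (1 − *w*) × *p*S,

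and a change in *w* moves it by (*p*H − *p*S) times that change.

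Inputs: *w* = 5% is the share of metastatic CRC given in Section 5.4.7; the other shares are assumptions. *p*H = 20% and *p*S = 2% are assumptions.

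| MSI-H share | Calculation | Pooled ORR |
|---|---|---|
| 0% | 0 + 1.00 × 2 | 2.0% |
| 5% | 0.05 × 20 + 0.95 × 2 = 1.0 + 1.9 | 2.9% |
| 25% | 0.25 × 20 + 0.75 × 2 = 5.0 + 1.5 | 6.5% |
| 50% | 0.50 × 20 + 0.50 × 2 = 10.0 + 1.0 | 11.0% |
| 75% | 0.75 × 20 + 0.25 × 2 = 15.0 + 0.5 | 15.5% |
| 100% | 1.00 × 20 + 0 | 20.0% |

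Each 10-point change in share moves the pooled ORR by 0.10 × (20 − 2) = 1.8 points.

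Range over other assumed rates:

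| Assumed MSI-H / MSS ORR | Pooled at 5% share | Pooled at 50% share |
|---|---|---|
| 30% / 2% | 3.4% | 16.0% |
| 20% / 2% | 2.9% | 11.0% |
| 15% / 5% | 5.5% | 10.0% |
| 10% / 0% | 0.5% | 5.0% |
| 5% / 5% | 5.0% | 5.0% |

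The last row shows the limit of the concern: with equal rates the mix does not matter.

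Median DOR is affected in its own way because it uses responders only. At 20%/2%, the MSI-H share of responders is 1.0/2.9 = 34% when 5% of the cohort is MSI-H, and 10.0/11.0 = 91% when half is. ORR and DOR for the same CRC cohort can then describe differently composed groups.

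**Price of splitting.** Suppose a cohort of 30 (assumed) with 6 responses: 6/30 = 20%, exact 95% CI 7.7% to 38.6%. If this were 5/15 in one group and 1/15 in the other, the exact intervals would be 11.8% to 61.6% and 0.2% to 31.9%. The intervals are wider, but each refers to a defined population.

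**The case against.** Four points can be made on the other side.

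- **Only a summary is visible.** Section 10.3 presents its analyses as a summary and leaves the selection of participants to a statistical analysis plan to be finalized before database lock, which is not among the documents. The ORR definition refers to an undefined population of interest, which leaves room for subgroups. This stands as a reason to ask for wording. It does not change the table, which names its unit and shows no CRC split.
- **Mixing is permitted, not planned.** Section 5.4.7 says these populations may be chosen, and Section 5.1.3.3 says efficacy may be explored. The sponsor could open only one CRC population. This stands, and it makes the conclusion conditional.
- **The two-stage decision.** A reader might infer that the Part C go/no-go decision for CRC also rests on the mixed rate. The documents do not support that as a finding. The design table and parts of Section 10.1.2 are blacked out and could hold separate CRC rows or historic rates. Any go probability would need an invented design.
- **TNBC.** A reader might infer that the TNBC estimate equally pools PD-(L)1-exposed and naive participants. Criterion 2h(ii) asks for "at least 1 standard chemotherapy regimen containing anthracycline and taxane" and further treatment for advanced disease, and is silent on anti-PD-(L)1 therapy; Section 6.2 allows prior immune therapy after a washout. So mixing is possible. But no text plans it, and Section 5.4.7 says no immuno-oncology agent is approved for TNBC. A split by exposure would also not show whether a response in a single-arm combination cohort came from nivolumab alone. This part survives only as an optional descriptive row.

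**Conclusion.** The concern holds for CRC reporting. Followed as written, Table 10.3.1-1 yields one CRC ORR, DOR and PFS summary over two populations that the protocol itself distinguishes by biology and by prior-treatment rule. The estimate then depends on the mix if both groups are enrolled and their rates differ. Under assumed ORRs of 20% and 2%, it ranges from 2.9% at a 5% MSI-H share to 11.0% at 50%. The true size in this trial cannot be computed, because neither the subgroup rates nor the enrolled mix is given.

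The conclusion does not extend to a claim that the two-stage rule is applied to a pooled CRC cohort, or that TNBC results are confounded by prior exposure. ORR is a secondary endpoint in a Phase 1/2 study, so this is a matter of making a preliminary activity estimate interpretable. It does not affect the primary safety objective.

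**What to change.** In Table 10.3.1-1 and in the statistical analysis plan:

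1. Report CRC ORR with exact 95% CI, median DOR and PFS rates separately for MSI-H/MMR-D and for MSS participants, using the status required at entry.
2. State which CRC population the historic ORR and the two-stage rule refer to, if the blacked-out design table does not already say so.
3. Optionally, add a descriptive TNBC row by prior anti-PD-(L)1 exposure, after checking that this exposure is captured. The documentation rule in criterion 2i covers RCC, CRC, NSCLC and SCCHN only.

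Running the full two-stage rule in each CRC subgroup is not asked for. It would need a full sample per subgroup, which is a change to the design and not to the reporting.

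The cost is a few lines of wording and some added table rows, with no new data for CRC. The downside is wider intervals within each subgroup, and a small MSI-H group may support little more than a count of responders.

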10.3.2 Safety Analyses

All safety analyses will be performed on the treated population.

Endpoint	Statistical Analysis Methods
Incidence of AEs, SAEs, AEs meeting protocol defined DLT criteria, AEs leading to discontinuation, and death	DLT rate by dose level, frequency distribution of treated participants with AE using the worst CTC grade. Participants will only be counted (1) once at the PT level, (2) once at the system organ class level, and (3) once in the 'total participant' row at their worst CTC grade, regardless of system organ class or PT.
Laboratory abnormalities Laboratory values will be graded according to CTCAE v4.03.	Laboratory shift table using the worst CTC grade on treatment per participant

[figure not shown]
Abbreviations: AE, adverse event; CTC, common terminology criteria; CTCAE, common terminology criteria for adverse events; DLTs, dose-limiting toxicities; PT, preferred term; SAE, serious adverse event.

Protocol Amendment No.: 07

10.3.3 Pharmacokinetic Analyses for BMS-986258 and Nivolumab

Parameters will be reported separately in Parts A, A1, and B in Cycle 1.

Endpoint	Statistical Analysis Methods
BMS-986258	
Parameters and Plots to Be Reported Separately for Cycle 1	in Parts A, A1, and B
Cmax, AUC(0-T), AUC(TAU), Ctau	Summary statistics: geometric means and coefficients of variation
Tmax	Summary statistics: medians and ranges
Parameters that May potentially be Assessed Following the B	Dose Administration for Cycle 3 in Parts A and
CLT, Css-avg, AI_AUC, and T-HALFeff_AUC	Summary statistics: geometric means and coefficients of variation
Cmax, AUC(TAU)	Scatter plots versus dose for each cycle measured; dose proportionality based on a power model and a CI around the power coefficient

Summary statistics will be tabulated for each PK parameter, if feasible, and wherever applicable, by treatment and dosing regimen. PK time-concentration data may be pooled with data from other studies for PPK analysis, which will be presented in a separate report.

Protocol Amendment No.: 07 Date: 16-Jun-2021

10.3.4 Immunogenicity

[figure not shown]
Endpoint	Statistical Analysis Methods
• Incidence of ADA to BMS-986258 • Baseline ADA-positive participant is defined as a participant who has an ADA-detected sample at baseline. ADA-positive participant is a participant with at least 1 ADA-positive sample relative to baseline after initiation of the treatment	Frequency distribution of BMS-986258 baseline ADA-positive participants and ADA-positive participants after initiation of the monotherapy and combination treatment

Abbreviations: ADA, anti-drug antibody.

^a Baseline sample is the last sample before initiation of the treatment.

Protocol Amendment No.: 07 Date: 16-Jun-2021

10.3.7 Other Analyses

Other exploratory analyses will be described in detail in the Statistical Analysis Plan finalized before database lock. Summary of OS rate will be analyzed similarly to PFS rate.

10.3.8 Interim Analyses

The expansion phase of this study employs a 2-stage design framework. Therefore, there will be an interim analysis planned when an adequate number of treated participants have available tumor data. Additional interim analyses may also be performed for administrative purposes or publications. No formal inferences requiring any adjustment to statistical significance level will be performed.

Protocol Amendment No.: 07 Date: 16-Jun-2021

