9.1.1.2 Imaging and Clinical Assessment

Tumor assessments should continue on the protocol-defined imaging schedule regardless if dosing is delayed or discontinued. Changes in tumor measurements and tumor responses will be assessed by the same investigator or designee using RECIST v1.1 criteria. Investigators will report the number and size of new lesions that appear while on study. The time point of tumor assessments will be reported on the eCRF based on the investigator's assessment using RECIST v1.1 criteria (see Appendix 5 for specifics of RECIST v1.1 criteria to be used in this study). Assessments of PR and CR must be confirmed at least 4 weeks (28 days) after initial response. A BOR of SD requires a minimum of 49 days on study from date of first dose.

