2.3 Response Assessment

2.3.1 Evaluation of Best Overall Response

The best overall response is the best response recorded from the start of the study treatment until disease progression or the last response recorded, taking into account any requirement for confirmation and censoring rules regarding subsequent therapy. The patient's best overall response assignment will depend on the findings of both target and non-target disease and will also take into consideration the appearance of new lesions. Furthermore, depending on the nature of the study and the protocol requirements, it may also require confirmatory measurement.

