2.3.3 Best Overall Response

Best response determination of complete or partial response requires confirmation: Complete or partial responses may be claimed only if the criteria for each are met at a subsequent time point of ≥ 4 weeks (28 days) later. In this circumstance, the best overall response can be interpreted as in Table 2.3.3-1. When SD is believed to be best response, it must meet the protocol specified minimum time from the date of first treatment or randomization date.

For example, if the first scheduled follow-up imaging visit is Week 6 (\pm 7 days) for a particular protocol, a Best Response of SD can only be made after the subject is on-study for a minimum of 6 weeks (42 days) minus 7 days, for an absolute minimum time on-study of 35 days from the reference start date (reference date is considered Day 1 on study). If the subject is not on-study for at least this amount of time, any tumor assessment indicating stable disease before this time period will have a Best Response of NE unless PD is identified.

Special note on response assessment: When nodal disease is included in the sum of target lesions and the nodes decrease to 'normal' size (< 10 mm), they may still have a measurement reported on scans. This measurement should be recorded even though the nodes are normal in order not to overstate progression should it be based on increase in size of the nodes. As noted earlier, this means that patients with CR may not have a total sum of 'zero' on the case report form (CRF).

Table 2.3.3-1:	Best Overall Response (Confirmation of CR and PR Required)	
Overall Response First Time Point	Overall Response Subsequent Time Point	Best Overall Response
CR	CR	CR
CR	PR	SD, PD OR PR ^a
CR	SD	SD provided minimum criteria for SD duration met, otherwise, PD
CR	PD	SD provided minimum criteria for SD duration met, otherwise, PD

Protocol Amendment No.: 07

Table 2.3.3-1:	Best Overall Response (Confirmation of CR and PR Required)	
Overall Response First Time Point	Overall Response Subsequent Time Point	Best Overall Response
CR	NE	SD provided minimum criteria for SD duration met, otherwise, NE
PR	CR	PR
PR	PR	PR
PR	SD	SD
PR	PD	SD provided minimum criteria for SD duration met, otherwise, PD
PR	NE	SD provided minimum criteria for SD duration met, otherwise, NE
NE	NE	NE
CR, complete response, PR, partial response, SD, stable disease, PD, progressive disease, and NE' inevaluable		

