2.3.4 Confirmation Scans

Verification of Response: To be assigned a status of CR or PR, changes in tumor measurements must be confirmed by consecutive or subsequent repeat assessments that should be performed no less than 28 days after the criteria for response are first met. Subsequent documentation of a CR may provide confirmation of a previously identified CR even with an intervening NE or PR (eg, CR NE CR or CR PR CR). Subsequent documentation of a PR may provide confirmation of a previously identified PR even with an intervening NE or SD (eg, PR NE PR or PR SD PR). However, only one (1) intervening time point will be allowed between PR/CRs for confirmation.

Verification of Progression: Progression of disease should be verified in cases where progression is equivocal. If repeat scans confirm PD, then progression should be declared using the date of the initial scan. If repeat scans do not confirm PD, then the subject is considered to not have progressive disease.

Protocol Amendment No.: 07

Approved v2.0

930120074 9.0

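### Does the Part C interim need a stated rule for responses still awaiting their confirmatory scan?

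*Combined protocol and SAP*

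**What the plan says.** Section 10.3.8 bases the Part C interim on the 2-stage design and says that "there will be an interim analysis planned when an adequate number of treated participants have available tumor data". It adds that "Additional interim analyses may also be performed for administrative purposes or publications". Neither sentence mentions confirmation.

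The response rules are elsewhere:

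- Section 10.3.1: "ORR is defined as the proportion of population of interest whose BOR is either CR or PR per RECIST v1.1".
- Appendix 5, Section 2.3.1: best overall response is determined "taking into account any requirement for confirmation and censoring rules regarding subsequent therapy".
- Section 9.1.1.2: "Assessments of PR and CR must be confirmed at least 4 weeks (28 days) after initial response".
- Appendix 5, Section 2.3.3: "Complete or partial responses may be claimed only if the criteria for each are met at a subsequent time point", with the same 28-day minimum.
- Appendix 5, Section 2.3.4: "Subsequent documentation of a PR may provide confirmation of a previously identified PR even with an intervening NE or SD", but "only one (1) intervening time point will be allowed between PR/CRs for confirmation".

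Section 7.4.1 keeps tumor assessments on an 8-week schedule from first dose. Section 9.1.1 allows extra scans when clinically indicated. Section 10.3.1 makes the treated population primary at the final analysis. It permits the response-evaluable set at interims with short follow-up, and Section 10.2 admits a participant to that set after a single post-baseline assessment.

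Section 10.1.2 bases the Part C sample size on ORR and refers to a 2-stage design that does not appear in the public copy. Section 10.3 leaves the selection of participants for analysis to the Statistical Analysis Plan.

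**The concern.** ORR drives Part C, and the interim exists because of the 2-stage design. A participant whose first response is seen shortly before the data cut is in the denominator but cannot yet be in the numerator. Table 2.3.3-1 in Appendix 5 covers a first CR or PR followed by another assessment, including one that is not evaluable. It has no row for a response whose next scan has not happened. If some participants had been scanned only once at the cut, interim ORR would understate what the same participants later show. A cohort could then look less active than it is, in the stage-1 review or in an interim publication.

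**Working it through.** **No plan figure to reproduce.** Stage sizes, boundaries and the null and target response rates are not in the public copy. Only the timing comes from the documents; the rest is illustration.

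**Timing.** A first response at Week 8 is confirmed at Week 8 + 8 = 16 on schedule, or from Week 8 + 4 = 12 if a clinically indicated scan is done. If the Week 16 scan is SD or not evaluable, a PR can still be confirmed at Week 24.

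**Share pending at a Week 8 cut.** Assume 15 participants, with the last at Week 8 when the data are cut and the other 14 spread uniformly over the preceding T weeks of accrual. All eventual confirmed responders first respond at Week 8, and confirmation takes g weeks. The last participant is pending, and each of the others is pending with probability g/T:

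pending = (1 + 14 × g/T) / 15; expected interim ORR = 25% × (1 − pending), where 25% is the assumed mature rate.

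| T (weeks) | Pending, g = 8 | ORR, g = 8 | Pending, g = 4 | ORR, g = 4 |
|---|---|---|---|---|
| 52 | (1 + 2.154)/15 = 21.0% | 19.7% | (1 + 1.077)/15 = 13.8% | 21.5% |
| 32 | (1 + 3.5)/15 = 30.0% | 17.5% | (1 + 1.75)/15 = 18.3% | 20.4% |
| 20 | (1 + 5.6)/15 = 44.0% | 14.0% | (1 + 2.8)/15 = 25.3% | 18.7% |

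**Later first responses.** Let first responses fall 60/30/10% at Weeks 8/16/24, with g = 8. For each response week, the same accrual model gives the share already seen and the share already confirmed; pending is the difference. For T = 52, 32 and 20:

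- Week 8 cut: seen 0.902, 0.857, 0.787; confirmed 0.718, 0.583, 0.392; pending 18.4%, 27.3%, 39.5%.
- Week 16 cut: seen 0.979, 0.970, 0.956; confirmed 0.902, 0.857, 0.787; pending 7.7%, 11.3%, 16.9%.

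Requiring two scans reduces the problem but does not remove it.

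**Dependence on the assumed rate.** The only ORR that the documents give for a TIM-3 plus PD-1 combination is 4.7% (Section 3.3; a different antibody, across indications). At that rate the 21.0% to 44.0% pending shares remove 4.7 × 0.210 = 1.0 to 4.7 × 0.440 = 2.1 percentage points. In 15 participants this is about 0.15 to 0.31 of a responder.

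**The opposite convention.** If pending responses are counted and only a fraction c later confirm, then with every response still pending a mature ORR of 20% reads as 20%/c. That is 25% at c = 0.8 and 33.3% at c = 0.6.

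**Analysis set.** Take 15 treated, 1 unscanned, 2 confirmed and 1 pending. ORR is 2/15 = 13.3% in the treated set and 2/14 = 14.3% in the response-evaluable set. If the pending response later confirms, these become 3/15 = 20.0% and 3/14 = 21.4%. Both sets read low, so the choice of set is not the cause.

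**Cost of waiting.** Relative to a Week 8 cut, two scheduled scans add up to 8 weeks. Awaiting confirmation of a first response at Week 16 adds up to 16 weeks, and 24 if an SD or non-evaluable scan intervenes.

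**The case for a change.** The strongest case for a change is that the protocol itself foresees interims with short follow-up and admits participants to the response-evaluable set after one scan. The confirmation rule then produces the low reading rather than preventing it. The Statistical Analysis Plan is promised only before database lock, with no stated timing relative to the interim. The 2-stage text, even if complete, need not cover the administrative or publication interims. The remark in Section 10.3.8 that no formal inference needing adjustment will be made concerns significance levels and does not make an immature ORR unbiased. A sentence would cost little.

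Part of this stands. Section 10.3.8 has no sentence on pending responses, Table 2.3.3-1 has no row for them, and the timing arithmetic is right.

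It does not establish a defect:

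- The trigger leaves the number of participants and the maturity of their data open; nothing in it directs a cut at one scan.
- The low reading depends on applying the Appendix 5 rule literally. In that case handling is settled, and what remains is ordinary immaturity. If the rule is not applied, the bias can run upward, so a downward direction cannot simply be asserted.
- The study is open-label and each time-point assessment is entered on the eCRF (Section 9.1.1.2). The sponsor can therefore see a PR awaiting confirmation alongside the confirmed count.

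**Conclusion.** No change follows. This is a detail that analysts fill sensibly, in the part of the plan where the design text is not public. Section 10.1.2 refers to 2-stage characteristics that the public copy lacks, and Section 10.3 assigns participant selection to the Statistical Analysis Plan. Either may already fix stage-1 evaluability and follow-up, so absence cannot be inferred.

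The remaining choice is a fair trade-off. Treating pending responses as non-responses reads low, counting them reads high, and waiting delays the interim by up to 16 to 24 weeks relative to a Week 8 cut. The documents do not require any one of these. An analyst reporting an immature ORR can show it with pending responses counted each way, without a protocol change.

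The illustrated loss of about 5 to 11 percentage points (25% falling to 19.7% or 14.0%) rests on an assumed 15 participants, a 25% mature rate, uniform accrual, all first responses at Week 8, confirmation at the next scheduled scan and a cut at the last participant's first scan. With the mature rate at 4.7% and the other assumptions unchanged, it is 1.0 to 2.1 points. Neither the actual size of the bias nor any effect on the stage-1 decision can be derived from the documents.
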